The long-term goal of this research is to use mechanisms identified via a fully-powered mechanistic RCT funded by NIH K23 or VA CDA to optimize a resilience-based, trauma-informed MBI. In order to secure funding and conduct this mechanistic RCT, feasibility and acceptability of the stressor paradigm and concurrent physiological data collection, as well as the MBSR and randomization procedures must be established.

4) Study Design

The design of this study is a randomized controlled interventional study. All participants will complete three in-person lab visits, consisting of computerized questionnaires, physiological data recording, and completion of a stressor paradigm. Following completion of computerized questionnaires at the baseline visit, participants will be randomized at a 1:1 ratio using covariate adaptive randomization.

Participants will be randomized to receive Mindfulness-Based Stress Reduction (MBSR; active intervention condition) or Health and Wellness Education (HWE; control condition). Both interventions include 8 weekly in-person group sessions with an additional extended session after week 8.

5) Study Population

a) Number of Subjects

This is a single center study. We will screen approximately 40 patients of which we expect to enroll 20 participants, all of whom will be veterans experiencing PTSD symptoms (PTSD symptoms will be confirmed during telephone screen). Therefore, 20 participants will sign the consent form and be included in this study.

b) Inclusion and Exclusion Criteria

Participants will be screened over phone to determine eligibility. Subjects will be aged 18-85 years. Subjects older than 85 years of age will be excluded due to their decreased ability to tolerate the experimental procedures because of potential cognitive decline and inability to sustain the attention needed for the Portland Arithmetic Stress Task (PAST), as well as the decreased ability to remain still during the intervention conditions due to musculoskeletal aches and pains and decreased flexibility frequently seen in aging.

Inclusion criteria	Exclusion criteria
Adult (18-85 years)	Pregnancy
Military veteran	Severe untreated depression, cognitive impairment, or active suicidality*
Experiencing PTSD symptoms	Life-threatening or severely disabling medical conditions
Reading and speaking in English	Excessive use of alcohol, nicotine, or cannabis†

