Abbreviated Posttraumatic Stress Disorder Checklist (PCL-6), depression (PHQ-9), suicidality (PHQ-9 item 9), substance use (Alcohol Use Disorders Identification Test; Cannabis Abuse Screening Tool; Fagerstrom Nicotine Dependence Scale), medical history, self-reported medication history, current mindfulness practice, historical mindfulness experience.
Demographics
Age, gender, sex, ethnicity, BMI, marital status, education, income, employment status, military branch, era of service, years enlisted.

Upon arrival at the research lab in Hatfield Research Center (HRC) for the first study visit, study personnel will review the study consent form with the participant and solicit questions. Once the subject verbally confirms understanding and interest in participation, they will be asked to sign consent forms and will be provided copies prior to leaving the HRC building. All research activities, including interventions, will take place at OHSU. Data collection and analysis will take place in the [name] Lab in OHSU's Hatfield Research Building, and interventions will take place at OHSU's Kohler Pavilion.

Subjects will be encouraged to ask questions throughout the duration of participation.

Modifications to the Consent Process

In this study, Veterans will primarily be recruited when they see a flyer and contact the study team. The PI will not be accessing the VA electronic medical record to identify a potential patient. Once a potential participant reaches out to the PI and study from the contact information provided in the flyer, the PI or a delegated study team member will review the initial phone script to understand if the participant meets eligibility and shows interest in participation. If the veteran is interested, the study team will call the participant at an agreed upon time to conduct screening procedures over phone. If the participant is eligible, the participant will be invited to sign the OHSU informed consent form prior to randomizing to the study intervention (MBSR or HWE).

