Stress induction: **1. Baseline:** The Simple Reaction Task (SRT) will serve as a baseline for the stressor task. Participants press a key each time a number appears on the screen. The SRT has been used as a baseline for cognitive stressors in prior [name] lab studies; **2. Stress induction:** The Portland Arithmetic Stress Task (PAST)⁷⁰ is a cognitive stressor comprised of arithmetic problems titrated in difficulty. It has an adaptive failure algorithm, maintaining an error rate of ~40%. It has been shown to induce physiological stress across groups.⁷⁰⁻⁷²

Aim 3 – Quantitative data will be collected on paper and entered in REDCap by a study team member on an [name] lab computer and in-person clinical interview (i.e., Clinician-Administered PTSD Scale for DSM-5 [CAPS-5]). Using this data, we will examine sensitivity and responsiveness to change of outcomes. This Aim will be conducted in accordance with best practice guidelines,^{73,74} CONSORT recommendations,⁷⁵ and previous research.^{76,77} **Sensitivity** in both groups will be analyzed via relative efficiency; dividing the *F*-statistic for each physiological (systolic and diastolic BP) and self-report (psychological resilience and PTSD symptoms) by the largest *F*-statistic among outcomes (see Table below for measures).^{77,78} This process will clarify which outcomes are most sensitive to MBSR. To generate *F*-statistics for relative efficiency, we will conduct repeated measures ANOVAs for each outcome in both groups. **This statistical approach focuses on the degree to which measures are sensitive, not whether change is significant.** **Responsiveness to change** over time will be assessed in the MBSR group for physiological and self-report outcomes by: 1) calculating and comparing standardized mean response by subtracting baseline mean response from post-intervention mean response, and dividing by standard deviation of change^{74,79,80} and 2) examining zero-order correlations between a global impression of change measure (post-intervention) and change scores (baseline to post-intervention) for self-report outcomes.⁸¹⁻⁸³

Primary measures to be collected are listed below:

Method	Variable	Measurement Tool	Timepoints
Paper>REDCap	Psychological resilience	Brief Resilience Scale (BRS)	Pre, mid, post
Paper>REDCap	PTSD symptoms	PTSD Symptoms Checklist for DSM-5 (PCL-5)	Pre, mid, post
Paper>REDCap	Mindfulness	Five Facet Mindfulness Questionnaire (FFMQ-15)	Pre, mid, post

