Potential participants will be sent a MyChart recruitment invitation and a follow-up (as applicable) via an email notification, as below, with the Subject "New Research Study" instructing them to log into MyChart to learn more and respond. The text of this invitation is included in the eIRB submission. The link in the MyChart invitation will take the potential participant to their MyChart homepage with a link to a description of the study. Potential participants will express interest or decline by pressing the associated buttons in MyChart, or they will not respond. If the potential participant indicates interest, they are automatically associated to the study in Epic with a status of "interested;" the study remains listed on the patient's Research Studies page in MyChart, and the study team immediately receives an in-basket notification in Epic so that they can follow up with the patient. If the patient clicks "No, Thank You" this study will no longer appear on their Research Studies page in MyChart, and the patient is automatically associated to the study in Epic with a status of "declined." When the participant expresses interest, the study team will call the participant to schedule the initial phone call for an initial review of eligibility and a second screening phone call before the participant is enrolled on study. Details of the initial and second phone call are included under "recruitment methods" section.

Please see below for a description of the study schedule. All survey data will be captured in paper surveys from study participants and will be directly entered in the REDCap database by a study team member.

Study Schedule:

Visits	Initial phone call 1	Screening phone call	Lab visit 1	Wk 1 ^e	Wk 2	Wk 3	Wk 4	Wk5/ Lab visit 2	Wk 6	Wk 7	Wk8/ Lab visit 3	Retreat	Post-intervention Wk9
Study overview and eligibility review	X												
Screening questionnaires ^a		X											
Demographics ^b		X											
Informed consent			X										
MBSR/HWE ^d intervention				X	X	X	X	X	X	X	X	X	
Study Visit Questionnaires ^c			X					X			X		
Clinical interview (Clinician administered PTSD scale for DSM-5 (CAPS-5)			X					X			X		
CareTaker VitalStream™ (physiologic data collection, BP)			X					X			X		
Lab Stressor			X					X			X		
Focus group Qualitative interview													X
Approximate total time	15 mins	30 mins	120 mins	150 mins	150 mins	150 mins	150 mins	270 mins	150 mins	150 mins	270 mins	7 hours	120 mins

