- a. Screening measures will include: PTSD (PCL-5), depression (PROMIS), suicidality (PHQ-9), substance abuse (Alcohol Use Disorders Identification Test, Cannabis Abuse Screening Tool, Fagerstrom Nicotine Dependence Scale) in addition to review of eligibility
- b. Demographic information includes age, gender, sex, ethnicity, BMI, marital status, education, income, employment status, military branch, era of service, years enlisted. Medical and medication history, current and historical mindfulness experience are captured during screening
- c. Questionnaires include Brief Resilience Scale, PTSD Symptoms Checklist for DSM-5 (PCL-5,6), UCLA Loneliness Scale, CAPS-5, Five Facet Mindfulness Questionnaire (FFMQ-15), Perceived Stress Scale (PCL-10), Distress tolerance scale (DTS)
- d. Participants are randomized at visit 1 to either MBSR or HWE. All participants have 30-minute practice assignments to be carried out every day at home.
- e. Week 1 of the interventions will occur within one week of completing Lab Visit 1 for all participants.

Participants may be withdrawn from this study without their consent in order to protect them from excessive risk (e.g., if they demonstrate unsafe elevated blood pressure), or in order to maintain the integrity of the study and data (e.g., a participant is not following study procedures and/or may be deliberately providing false information).

7) Data

Handling of Data

Data collected will include computer-based and physiological recordings listed above, as well as demographic data such as age and gender. Data will also include health status information, such as

medical conditions and prescription medications for use in determining eligibility. All data will be stored on a restricted OHSU network drive in a limited access folder or in a REDCap database, and the study PI and designee will be responsible for storage and transmission of the data. Following this study, all data will be transferred and stored indefinitely in repository IRB #7436. No specimens will be collected as part of this study.

a) Sharing of Results with Subjects

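### Randomisation is placed after the baseline questionnaires only, so the arm may already be known when the Lab visit 1 blood pressure baseline for Aim 3 is recorded

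*Combined protocol and SAP*

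**What the plan says.** Section 4 (Study Design) describes "three in-person lab visits, consisting of computerized questionnaires, physiological data recording, and completion of a stressor paradigm". Its next sentence fixes the randomisation point by the first of those three parts: "Following completion of computerized questionnaires at the baseline visit, participants will be randomized at a 1:1 ratio using covariate adaptive randomization".

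The rest of the document adds little about order:

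- Study Schedule, note d: "Participants are randomized at visit 1 to either MBSR or HWE". No position within the visit is given.
- Study Schedule, table: questionnaires, CAPS-5, VitalStream recording and stressor are all marked at Lab visits 1, 2 and 3. There is no randomisation row and no stated order within a visit.
- Study Schedule, note e: "Week 1 of the interventions will occur within one week of completing Lab Visit 1 for all participants".
- Modifications to the Consent Process (section 5): signed consent comes before randomisation. No outcome assessment is mentioned.
- CAPS-5: note c has "Questionnaires include Brief Resilience Scale, PTSD Symptoms Checklist for DSM-5 (PCL-5,6), UCLA Loneliness Scale, CAPS-5" in one list, but section 6 and the schedule table treat CAPS-5 as a separate clinical interview.

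The primary measures table in section 6 lists BP at pre, mid and post. For Aim 3, sections 6 and 8 calculate a standardised response in the MBSR group (post-intervention mean minus baseline mean, over the SD of change). They also rank SBP, DBP and the self-report outcomes by each F-statistic relative to the largest.

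**The concern.** A baseline is best recorded before anyone present knows the assignment. Here that holds for the self-report questionnaires, because randomisation follows them. It is not secured for BP, and it is unclear for CAPS-5. Note e keeps Lab visit 1 ahead of treatment, but not ahead of knowledge of the arm.

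Aim 3 compares outcomes with one another. If a participant's BP responds to learning the assignment, the BP baseline carries that response and the self-report baselines do not. The BP change score, its standardised response and its place in the F-ratio ranking could then differ for a reason unrelated to how sensitive the measure is. That ranking is meant to inform the choice of outcomes for the later mechanistic trial, and the randomisation procedure is itself one of the things being tested for that trial.

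**Working it through.** **Step 1. Does any passage close the gap?**

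| Place | What it fixes | Does it put BP before allocation? |
|---|---|---|
| Section 4 | Randomisation follows the questionnaires | No |
| Note d | Randomisation is at visit 1 | No |
| Note e | Week 1 follows completed Lab visit 1 | No; it concerns treatment only |
| Consent section | Consent precedes randomisation | No |
| Schedule table | All assessments at visit 1, no order | No |

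No passage delays disclosure or masks participants or assessors. A visit run as questionnaires, allocation, BP and stressor complies with every statement. So does a visit with allocation last.

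**Step 2. How would a shift enter Aim 3?** The plan states no figure to reproduce. Let b be the mean shift in MBSR baseline BP from knowing the arm, r the fraction of it still present at visit 3, and SD the standard deviation of change.

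- Baseline taken after allocation: the standardised response moves by (r·b − b)/SD = −(1 − r)·b/SD.
- Baseline taken before allocation: it moves by r·b/SD.
- With r = 0 these are −b/SD and 0. With r = 1 they are 0 and b/SD.
- If BP is scored as stressor minus reaction-task baseline and both readings shift equally, b cancels and both expressions are 0. Section 3 describes physiological resilience partly as not shifting away from baseline, which would fit that scoring. Sections 6 and 8 name only systolic and diastolic BP, so scoring by level is not excluded.

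**Step 3. Illustrative size.** Only the number randomised and the attrition rate come from the document.

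- n: 20 randomised 1:1 gives 10 in MBSR. Applying the 21.3% attrition quoted in section 3: 10 × (1 − 0.213) = 7.9, taken as 8.
- SD of BP change: assumed 8 to 12 mmHg.
- Standardised response s: assumed 0 to 0.5.
- Effect of 1 mmHg when r = 0: 1/8 = 0.125; 1/10 = 0.100; 1/12 = 0.083.
- Standard error = √(1/n + s²/(2n)):
  - n = 10, s = 0: √0.1 = 0.316
  - n = 10, s = 0.5: √(0.1 + 0.0125) = 0.335
  - n = 8, s = 0: √0.125 = 0.354
  - n = 8, s = 0.5: √(0.125 + 0.015625) = 0.375
- Shift equal to one standard error = SE × SD: smallest 0.316 × 8 = 2.5 mmHg; largest 0.375 × 12 = 4.5 mmHg.

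The document gives no value for b or r, so the actual bias cannot be computed. The effect on the F-ratio ranking was not calculated.

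**The case against.** The strongest reply is that section 4 sets an earliest point, not a sequence. It does not say that allocation happens at once or that the arm is then disclosed. Its wording is also loose: it calls the questionnaires computerised, while section 6 has them on paper and entered in REDCap by staff. This stands. A reader might infer that BP is recorded after randomisation, because questionnaires are listed first in section 4 and in the schedule rows. Neither list is stated to be in time order, so the document shows only that this order is permitted.

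Second, no harm is demonstrated. Aim 3 is descriptive, the trial has 20 participants, and nothing in the document suggests that BP reacts to allocation. This also stands, and it limits the point to a possible bias.

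Third, participants attend their assigned groups well before visits 2 and 3, so those readings are taken with the arm known whatever is changed. Step 2 shows the consequence: if the shift persists in full (r = 1), moving allocation later puts it into the change score instead of cancelling it. The change therefore cannot be said to remove every effect of knowing the arm. What remains is the ordinary reason for a pre-allocation baseline: any reaction to assignment then falls after baseline for every outcome alike.

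Fourth, on note c's wording CAPS-5 already precedes randomisation. That is one reading; section 6 and the schedule support the other.

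A reader might also infer that the Aim 2A stress-induction test is compromised. The plan says "The Simple Reaction Task (SRT) will serve as a baseline for the stressor task", and the test is within participants. It would be biased only if knowing the arm moved the two readings differently, and nothing in the document suggests that.

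**Conclusion.** The point holds as a permitted weakness in the order of Lab visit 1. As written, the plan allows the Aim 3 baseline SBP and DBP, and possibly CAPS-5, to be collected with the arm known, while the self-report baselines are not. It does not show that this happens, and it does not show that the results would be biased.

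The size is unknown and may be zero. Under the assumed SDs, and a shift that has gone by visit 3, about 2.5 to 4.5 mmHg would be needed to equal one standard error of the MBSR standardised response. A smaller shift would be hard to tell from sampling noise in an arm of 8 to 10. The case for the change is that it puts all outcomes on the same pre-allocation footing for very little effort. The change is worth making, but the trial does not stand or fall by it.

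**What to change.** In section 4, replace the condition that opens the randomisation sentence so that allocation follows completion of all Lab visit 1 assessments: questionnaires, CAPS-5, VitalStream recording and stressor. Leave the 1:1 ratio and the covariate-adaptive method as they are. In schedule note d, change visit 1 to the end of visit 1. Naming CAPS-5 explicitly settles its position whether or not it is counted as a questionnaire.

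The cost is a short text amendment, which section 9 requires to go to the IRB before it is implemented. Allocation stays within the same visit, and note e already starts week 1 after that visit is complete, so the schedule does not move. Any questionnaire scores used as randomisation covariates are still available at the later point. No visits or data are added. If staff already randomise last, the edit simply records the practice.

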Be able to travel to OHSU for three two-hour lab visits, 8 weekly intervention sessions and one long extended session, and a two- hour focus group	

* Severe cognitive impairment will be determined by a score ≤ 20 on the Telephone Interview for Cognitive Status; active suicidality will be determined by endorsement of item 9 on the Patient Health Questionnaire.

† Alcohol use will be determined by a score ≥ 8 on the Alcohol Use Disorders Identification Test (AUDIT-C); excessive cannabis use will be determined by a score ≥ 7 on the Cannabis Abuse Screening Tool; excessive nicotine use will be determined by a score ≥ 8 on the Fagerstrom Nicotine Dependence Scale.

If a participant does not consent, or is excluded for any other reason (e.g. screen-failed), data already collected (e.g., demographic; screening data) will be retained for the purpose of characterizing individuals who made contact, as well as collecting and presenting feasibility and acceptability data to the VEG at the conclusion of this study. The reason for not enrolling will be noted.

c) Vulnerable Populations

No vulnerable populations will be recruited as part of this study.

d) Setting

This is a single site study. All research activities, including interventions, will take place at OHSU with the exception of some recruitment procedures that will take place at the Portland VA (e.g., presenting study materials to clinics).

e) Recruitment Methods

A multi-dimensional recruitment strategy will be used to achieve target enrollment numbers. We will use OHSU approved recruitment tools such as Epic Reporting Workbench, Slicer Dicer, Research Data Warehouse (RDW), etc., to query OHSU electronic medical records. This study will use Epic MyChart® to recruit potential participants. Researchers will use OHSU approved search tools as mentioned above to identify potential study participants. Potential participants will be sent a MyChart® recruitment message asking them to participate. There is no risk of duplicate invitations as it is based on MyChart® accounts combined with Epic records and no duplication is possible.

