At the completion of the study, if patients consent to sharing data in the repository, their data will be released to repository IRB #7436. See repository protocol for details about requesting, releasing, and labeling data.

10) Risks and Benefits

a) Risks to Subjects

The risk in participating in the present study is low. Participants may feel distress when reporting their PTSD symptoms or identifying their index trauma (i.e., the most salient trauma connected to their PTSD symptoms) as part of the administration of the Clinician-Administered PTSD Scale (CAPS-5). Participants may also feel discomfort or embarrassment when discussing their general experiences during the intervention conditions. They may also feel stress or frustration when completing the laboratory stressor paradigm. Participants have the right to withdraw, and may attend intervention groups and not actively participate, or may not complete MBSR home practice between sessions.

There is no discomfort associated with the collection of physiological data. The CareTaker™ device using a Velcro finger cuff attached with similar tightness to an arm cuff blood pressure monitor. A thin clear tube connects the finger cuff to a small wrist pack that houses the electronic components of the device. The CareTaker™ is completely wireless, and will relay data via Bluetooth connectivity to a tablet.

One of the potential risks of participation breach of confidentiality. It is possible that, if someone inadvertently obtained data, this could result in harm to research participants, with legal, financial, or emotional implications of the affected Veterans. We will take all possible measures to protect the security and integrity of personal health information.

b) Potential Benefits to Subjects

Veterans may find it rewarding to engage in group-based interventions in which they are encouraged to share their experiences with other veterans with similar struggles related to PTSD symptoms. They may similarly appreciate being able to share their perspectives regarding their ability and strategies for coping with symptoms. Participants may also experience reduction in symptoms of PTSD, depression, and anxiety as a result of participating in the MBSR condition.

REFERENCES

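### No depression or suicidality instrument is scheduled after the screening call, so two exclusions can be out of date at randomisation and later change is not systematically measured

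*Combined protocol and SAP*

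**What the plan says.** The exclusion list in Section 5(b) includes "Severe untreated depression, cognitive impairment, or active suicidality". Its footnote adds that "active suicidality will be determined by endorsement of item 9 on the Patient Health Questionnaire". The footnote gives no threshold for severe untreated depression.

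The instruments appear in two screening lists. The table under Consent Process gives "depression (PHQ-9), suicidality (PHQ-9 item 9), substance use". Note a to the Study Schedule in Section 6 gives "depression (PROMIS), suicidality (PHQ-9), substance abuse". The schedule row "Screening questionnaires ^a" carries a single mark, under the screening phone call.

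For the lab visits, note c begins "Questionnaires include Brief Resilience Scale, PTSD Symptoms Checklist for DSM-5 (PCL-5,6), UCLA Loneliness Scale, CAPS-5" and goes on to mindfulness, perceived stress and distress tolerance. The table of primary measures in Section 6 covers the same constructs plus blood pressure, at pre, mid and post. Neither list names a depression or suicidality measure.

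On safety, Section 6 allows withdrawal without consent to protect a participant from excessive risk, with unsafe blood pressure as its example. Section 9 assigns continuous data and safety monitoring to a study role and makes a neurologist available to review and refer adverse events that need medical intervention. Section 7(a) says that referrals rest on general critical blood-pressure values alone. Section 10(b) says: "Participants may also experience reduction in symptoms of PTSD, depression, and anxiety as a result of participating in the MBSR condition".

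**The concern.** Two conditions are judged serious enough to keep a veteran out, yet they are checked only by telephone, before the consent visit, at a time with no stated limit relative to randomisation. Staff who follow the plan exactly could randomise someone who no longer meets the entry criteria, and nothing scheduled at Lab visit 1 would reveal it.

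After that, participants repeatedly undergo procedures that Section 10(a) itself describes as possible sources of distress: an interview about the index trauma and a laboratory stressor. The plan sets a numerical trigger for blood pressure. It sets no corresponding measurement for the psychiatric risks on which it excludes. Individual safety is the main thing at stake. A secondary loss is that a feasibility study meant to prepare a larger trial would have no description of depression or suicidality beyond entry.

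**Working it through.** No sample-size, power or alpha figure bears on this point, and the plan states no figure to reproduce. The check is a comparison of lists and a count from the Study Schedule.

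**1. Where the screen is scheduled.** The schedule has 13 columns: initial call, screening call, Lab visit 1, Weeks 1 to 8 (8 columns, with Lab visit 2 in Week 5 and Lab visit 3 in Week 8), retreat and Week 9. That is 1 + 1 + 1 + 8 + 1 + 1 = 13. Screening questionnaires are marked in 1 column, the screening call. Columns after it: 13 − 2 = 11. Columns among those 11 with a depression or suicidality instrument: 0.

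**2. What happens in those 11 columns.**
- CAPS-5 interviews: 3 (Lab visits 1, 2 and 3).
- Stressor tasks: 3 (the same visits).
- Intervention sessions: 8 weekly + 1 retreat = 9.
- Focus group: 1.
- Scheduled time in minutes: 120 (Lab visit 1) + 4 × 150 (Weeks 1–4) + 270 (Week 5) + 2 × 150 (Weeks 6–7) + 270 (Week 8) + 420 (retreat) + 120 (Week 9) = 2,100, or 35 hours.

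**3. Length of the unmeasured period.** Note e places Week 1 within one week of Lab visit 1. Week 1 to Week 9 is 8 weeks, so Lab visit 1 to Week 9 is about 8 to 9 weeks. If the interval from the screening call to Lab visit 1 is *d* weeks, the time since the last scheduled measurement reaches about *d* + 8 to *d* + 9 weeks. The documents give no value or limit for *d*.

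**4. Lists side by side.**

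| Topic | One place | Another place |
|---|---|---|
| Depression tool at screening | Consent Process: PHQ-9 | Schedule note a: PROMIS |
| Suicidality tool at screening | Consent Process: PHQ-9 item 9 | Schedule note a: PHQ-9 |
| Depression or suicidality at lab visits | Primary measures table: none | Schedule note c: none |
| Referral | Section 7(a): blood-pressure values only | Section 9: adverse events reviewed and referred as needed |

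The two screening lists agree on the PHQ-9 for suicidality and disagree on the depression tool. The two visit lists agree that neither construct is measured. In its context the Section 7(a) sentence may concern physiological data only. Read literally, it conflicts with Section 9.

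**5. What by-arm reporting could show.** With 20 participants at 1:1, each arm has about 10. If 0 of 10 endorse an item, the exact two-sided 95% upper limit is 1 − 0.025^(1/10) = 0.31. A clean arm would still be compatible with a true rate near 31%.

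**The case against.** The strongest reply is that the plan does not leave participants unobserved. Section 9 provides continuous safety monitoring and adverse-event review, Section 6 permits withdrawal for risk, and staff meet participants at nine sessions and interview them at three lab visits. That stands. A reader might infer that emerging risk cannot be seen, or that detection depends entirely on the veteran volunteering it. The documents do not support this. They support only that risk is not systematically measured and that the general monitoring has no stated instrument, schedule or trigger.

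Other tempting readings also go too far:
- **Continuous exposure to trauma interviewing and stressors.** The CAPS-5 and the stressor each occur three times; only the group sessions are weekly.
- **A participant who becomes suicidal after randomisation breaches an exclusion.** Section 5(b) states entry criteria, and nothing applies them later. The eligibility argument reaches Lab visit 1 and no further.
- **Depression must be an outcome because Section 10(b) names it as a possible benefit.** It is not among the aims, and a possible benefit need not be an endpoint.
- **The trial loses an essential comparison of harm between arms.** At about 10 per arm such a comparison would say little.
- **Late data entry delays detection.** The plan says "All survey data will be captured in paper surveys from study participants" and are entered directly by staff. It states no delay.
- **No response exists for callers who endorse item 9.** The phone script is not part of these documents, so this cannot be concluded.

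It is also fair that the initial call uses eligibility questions whose content is not given, so a single asking is certain only for the named instruments. That call too precedes enrolment. Finally, the measure lists are not complete: the global impression of change measure used in the analysis appears in neither. If a PHQ-9 is already intended at the visits, the protocol should say so.

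**Conclusion.** The point holds as a gap in scheduled measurement. Two exclusions rest on a telephone screen with no stated limit on its age at randomisation, and 0 of the 11 later schedule columns contain an instrument for either. The period from Lab visit 1 to Week 9 is about 8 to 9 weeks, to which the unstated interval before Lab visit 1 must be added.

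This rests on two assumptions: that the visit lists are complete in this respect, and that no listed questionnaire or interview is meant to serve as the suicidality check (the documents assign that role to none of them). The case for change is individual safety and confirmed eligibility, not comparison between arms. It is a worthwhile, inexpensive improvement to a plan that already has general safeguards.

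**What to change.** 1. Add the PHQ-9 to the questionnaires at Lab visits 1, 2 and 3, in the primary measures table and in schedule note c. At Lab visit 1 it should be completed and looked at before randomisation, so that the existing exclusion is confirmed on the day. Section 4 already places randomisation after the baseline questionnaires, so the order of the visit need not change, and anyone found ineligible would leave before being randomised.
2. Summarise the PHQ-9 and item 9 descriptively only, with no test between arms.
3. Reconcile the depression screening tool (PHQ-9 under Consent Process, PROMIS in schedule note a), and state how severe untreated depression is determined. Until that is written, the recheck confirms the item 9 criterion but not the depression criterion.
4. Reconcile the Section 7(a) sentence on referrals with the monitoring and referral described in Section 9. How to respond to a positive item is for the study's clinicians and the IRB.

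The cost is a few minutes per visit, a member of staff looking at the form during the visit, and a protocol amendment. A consented participant may be found ineligible at Lab visit 1, so the Section 5(a) statement that 20 participants will sign consent and be included would need rewording.
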